### Randomization

Given the dose-escalating nature of the trial, volunteers will not be randomized but can choose in which group they wish to participate. Samples will be analyzed as they become available without any pre-defined order.

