6.4.1 Risk Assessment

The following section (Table 5) outlines the initial risk assessment and mitigation strategy for this study protocol.

Table 5. Risk Assessment

Important Potential/Identified Risk	Data/Rationale for Risk	Mitigation Strategy
Investigational study product (mAb TB31F)		
Important potential risk: First-in-human unknown risk	There is no prior experience of mAb TB31F or similar monoclonal antibodies to the Pfs45/48 malaria antigen in human subjects.	A dose escalating design will be used for Group 1 up till Group 4, starting with the lowest dose of 0.1 mg/kg. Study subjects will be observed closely by qualified clinicians, and emergency care will be immediately available to subjects. A minimum of 48 hours is required between product administration to the two sentinel subjects of each group. Group dose escalation will occur no sooner than 14 days according to the holding criteria.
Important potential risk: Hypersensitivity (including anaphylaxis)	As with other monoclonal antibody products, hypersensitivity and anaphylaxis to one or several components of the vaccine can rarely occur.	All study subjects will receive premedication. Subjects will be observed closely for at least 60 minutes following administration of the mAb TB31F product with appropriate medical treatment readily available in case of severe adverse events.
Study procedures		
Pain when taking blood samples	Because of the necessity to obtain frequent blood sampling for accurate PD/PK modeling, there is	Subjects will receive an intravenous catheter for frequent blood sampling. Subjects will be

	
a risk of feeling faint, or experience mild pain, bruising, irritation or redness at the site where blood was taken. The amount of blood to be taken for sampling will not be harmful to the subject's health (~400mLs)
	
advised to inform or call the study doctor immediately if they have any side effects.

Intravenous catheter placement	
The placement of an intravenous catheter in the subject's arm may cause the subject immediate pain at the site of catheter placement.
	
Experienced and qualified medical personnel will insert intravenous catheter and counsel the subject.

Pregnancy risks		

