8.3.11 Laboratory Evaluations

During the study, blood samples will be drawn for screening, safety and research purposes. The blood sampling schedule in the flowchart (section 8.3.18) shows the maximum amounts of blood that will be drawn. Following universal precautions, blood will be collected by venipuncture into vacutainer tubes. Blood specimens will be affixed with coded labels that link the specimen to the subject, specimen type, specimen collection date, and time-point. The specimen collection tube must be appropriate for the type of specimen required. The cumulative blood draw for each subject over the entire course of study participation is approximately 400mL.

Biological safety parameters will be measured on plasma or serum samples at the central laboratory of the RUMC. In the case where a laboratory assessment is outside the reference range, a decision regarding whether the result is of clinical significance or not shall be made by the investigator and shall be based, in part, upon the nature and degree of the observed abnormality. The assessment may first be repeated for confirmation. All abnormalities will be documented in the source documents, including clinical considerations.

Pharmacokinetic and functional analysis of transmission reduction activity

Pharmacokinetic (pK) sampling will establish the dose-response curve for each subject enrolled in this Phase 1 study. The serum concentrations of TB31F will be measured by an ELISA against a recombinant epitope R0.6C of the Pfs48/45 antigen at each sampling time point. Assessment of TB31F concentrations in the serum from subjects will be performed by the Human Immunology Laboratory at Imperial College London. Functional transmission-blocking activity will be determined at defined intervals as per protocol using SMFA assays performed at Radboudumc in Nijmegen the Netherlands

Complete Blood Count (CBC)

Complete hematology tests, including hemoglobin, hematocrit, red blood cell count, white blood cell count with differential (including neutrophils, basophiles, eosinophils, monocytes and

lymphocytes) and platelet count will be measured when appropriate. Complete hematology will be done at screening, at inclusion, at 24 hours and days 2, 7, 14, 21, 28 and 84.

Clinical Chemistry

Glucose will be measured only at screening. Alanine aminotransferase (ALT), aspartate aminotransferase (AST), creatinine, will be measured at screening, inclusion, at 24 hours and days 2, 7, 14, 21, 28 and 84.

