8.3.15 Standard Membrane Feeding Assay

Samples for SMFA will be collected from all subjects. Sera and/or purified IgG prepared from each serum will be used in the SMFA. Samples will be frozen until SMFA is planned. SMFA assays will be performed at both Radboudumc (The Netherlands) and the Laboratory of Malaria and Vector Research (LMVR), NIH USA, using a qualified standard membrane feeding assays using serum from subjects in cultures with *P. falciparum* and *Anopheles stephensi* mosquitoes.

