## Method

### Study design

TB31F is a first in human safety trial in healthy volunteers, designed to identify safety concerns associated with TB31F administration at different dosages. A total of twenty-five (n=25) healthy adults (males and females) aged 18 – 35 will be divided over five groups. Each group will include five subjects. Each group will receive a single dose of mAb TB31F administered by intravenous or subcutaneous infusion. Group 1 will receive 0.1 mg/kg TB31F i.v., Group 2 will receive 1 mg/kg TB31F i.v., group 3 will receive 3 mg/kg TB31F i.v., group 4 will receive 10 mg/kg mAb TB31F i.v. and group 5 will receive 100mg mAb TB31F subcutaneously. A step-wise approach will be taken.

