**Efficacy outcome analyses:**

- TB31F antibody prevalence and density will be determined by ELISA; the mean of duplicate concentration estimates is used for analyses. Antibody density will be expressed in µg/mL (outcome measure 6).
- TB31F antibody density will be plotted over time per individual and either as a mean or geometric mean per group. Mixed effects models may be used to investigate the interaction of timepoints and group on TB31F antibody concentration, allowing for subject specific random intercepts to control for the correlation within individuals (outcome measure 6).
- TB31F pharmacokinetics will be analyzed using standard non-compartmental methods to establish the maximum concentration ( $C_{max}$ ), terminal half-life ( $t_{1/2}$ ), area under the curve (AUC  $0-\infty$ ) and Volume of Distribution ( $V_d$ ) for each subject who received mAb TB31F. Additionally, the absorption rate constant ( $K_a$ ) will be determined for group 5 (subcutaneous administration). Geometric mean and geometric coefficients of variation of  $T_{1/2}$  and  $V_d$ , as well as of dose-adjusted  $C_{max}$  and AUC will be reported per dose group and overall (outcome measure 7).
- TRA will be quantified as the relative reduction in oocyst intensity for test samples (one feeder per test sample) compared to pooled naïve serum controls (two feeders). Samples may be tested in one or two independent SMFA experiments. TRA values for each participant and time-point will be estimated using generalized linear models, as previously described (outcome measure 8).

- We may calculate the percentage of individuals per group that have at least 50%, 80% and 90% TRA per timepoint and the percentage of individuals per group with statistically significant TRA at each timepoint. Mean TRA levels may also be calculated per study group per time point and compared between groups (outcome measure 8).

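### Testing samples in order of availability lets dose group and time point be confounded with SMFA run, and possibly laboratory, and the SAP states no run or laboratory term for TRA

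*SAP*

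**What the plan says.** - **Order of testing.** SAP, Randomization: "Samples will be analyzed as they become available without any pre-defined order". The sentence covers all samples and does not name the SMFA. The same section says that "volunteers will not be randomized but can choose in which group they wish to participate".
- **Calendar.** Protocol 6.4.1: "Group dose escalation will occur no sooner than 14 days according to the holding criteria". Table 2 in Protocol 3.1 gives the same minimum between every pair of successive groups, group 5 included.
- **Assay.** SAP, Efficacy outcome analyses: one feeder per test sample and two for the pooled naive control serum. "Samples may be tested in one or two independent SMFA experiments"; no rule says which samples get two.
- **Storage.** Protocol 8.3.15: "Samples will be frozen until SMFA is planned". Run size and composition are not stated.
- **Laboratory.** Protocol 8.3.15: "SMFA assays will be performed at both Radboudumc (The Netherlands) and the Laboratory of Malaria and Vector Research" at NIH. Protocol 8.3.11 describes functional activity as determined "using SMFA assays performed at Radboudumc in Nijmegen the Netherlands" and mentions no second site. The SAP names no SMFA laboratory.
- **Model.** TRA comes from generalized linear models defined by citation. The concentration-TRA fit uses mixed models resembling a cited method. The only random effect the SAP spells out is a subject intercept, and that is for antibody concentration. No run or laboratory term is written down for TRA.
- **Use.** Protocol 10.2 compares TRA between groups or time points by t-test or one-way ANOVA. The SAP may count subjects with at least 50%, 80% and 90% TRA, estimates inhibitory concentrations such as the IC80, and explores by simulation which regimens hold at least 80% TRA over a season.

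**The concern.** TRA is a ratio to a control. If control and test samples share a run, dividing by the control removes a shift common to that run. It also passes the control's own sampling error, from only two feeders, to every TRA calculated in that run. When a dose group is tested in one run, its five subjects share that error, so averaging over them does not reduce it. A t-test or ANOVA that treats the five values as independent does not see it.

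Testing in order of availability, with groups weeks apart, makes such a layout likely. Protocol 1.1 itself reports greater variability between experiments at 1.1-3.3 µg/mL, just where TRA falls below the 80% benchmark. At stake are group differences in TRA at lower activity, how long TRA stays above 80%, the threshold counts and the IC80. These could partly reflect the run or the laboratory.

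**Working it through.** **1. The plan's own figures.** The plan gives no SMFA variance, run size or power. Its one numerical design statement concerns safety with 20 subjects: 1 - (1 - 0.1087)^20 = 0.8999 and (1 - 0.0052)^20 = 0.9010, both matching the stated 90%. This point does not affect it.

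**2. Does testing as available separate the groups?** Inputs: the minimum intervals in Table 2, SMFA samples at pre-dose/end of infusion and days 7, 28, 56 and 84, and no use of visit windows. First doses then fall on days 0, 22, 40, 58 and 76. Suppose that a run takes all samples collected in a block of W consecutive days, averaging over where the block starts:

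| W (days) | Between-group pairs at the same time point sharing a run | Within-subject pairs from different sampling days sharing a run |
|---|---|---|
| 7 | 0% | 0% |
| 14 | 0% | 5% |
| 28 | 13% | 10% |
| 56 | 37% | 31% |

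If all sera are held to the end and mixed, no confounding is forced. Some separation has already happened. Protocol 13.2, written before group 5, reports TRA of about 50% for group 1 at end of infusion and above 95% for group 2 to day 28. Unless those sera are retested, any comparison of group 5 with those readings is between runs.

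**3. Size of the shared control error.** None of these assay inputs is in the documents; all are assumptions: 20 mosquitoes per feeder (40 over two control feeders), mean 20 oocysts, negative-binomial k = 2, and feeder SD s of log intensity from 0.1 to 0.3.

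Var(log control mean) = (1/20 + 1/2)/40 + s²/2 = 0.01375 + s²/2

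- s = 0.1: 0.01875, SD 0.137
- s = 0.3: 0.05875, SD 0.242

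95% range of observed TRA when a group is tested in one run = 1 - (1 - TRA) × exp(±1.96 × SD):

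| True TRA | s = 0.1 | s = 0.3 |
|---|---|---|
| 50% | 35-62% | 20-69% |
| 80% | 74-85% | 68-88% |
| 95% | 93-96% | 92-97% |

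With two independent experiments per sample, the SD falls by √2 to 0.097-0.171, and a true 80% reads 76-84% to 72-86%.

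**4. Can it explain the preliminary contrast between groups 1 and 2?** Residual transmission of 0.50 against at most 0.05 is a log ratio of at least ln 10 = 2.30. The difference of two independent control errors has SD √2 × 0.137 = 0.19 to √2 × 0.242 = 0.34. The contrast is at least 2.30/0.34 = 6.8 SDs. It cannot.

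**5. Effect on the planned tests if each group is its own run.** Assume equal feeder variance on the log scale for test and control, so the shared variance is half a feeder variance, and let between-subject variance be q times the feeder variance. With "Each group will include five subjects", the between-group variance is inflated by 1 + 5 × 0.5/(1 + q). For the two-group t-test (8 df), the true error rate is P(|t| > 2.306/√inflation):

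- q = 0: inflation 3.5, error 0.25; five-group ANOVA 0.53
- q = 1: inflation 2.25, error 0.16; ANOVA 0.31
- q = 4: inflation 1.5, error 0.10; ANOVA 0.15

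Simulation with one subject of each group per run, and run as a block, gave 0.050-0.052 for two groups and 0.049-0.051 for five. The same layout without the run term made the two-group test conservative (0.024-0.042).

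**The case against.** A reader might infer that the plan necessarily aliases dose group with run. The documents do not support that. The order sentence does not name the SMFA, sera are frozen until the assay is planned, run size is not given, and visits of different groups overlap in calendar time. Mixed runs are possible. What stands is that nothing requires them, and the one stated rule points the other way.

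A reader might also infer that the models ignore run. The methods cited for the generalized linear and mixed models could not be checked and may contain an experiment term. It stands only that the SAP does not state one.

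On laboratories, Protocol 8.3.11 names one site without saying it is the only one. That is an ambiguity, not a flat contradiction.

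The SAP has partial mitigation. It acknowledges poor precision below about 80% TRA, allows TRA to be inferred from concentration, and permits a second experiment. The second experiment shrinks the shared error; the concentration fit is estimated from the same TRA readings.

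Finally, TRA is secondary and group comparisons are acknowledged as unpowered. That limits the weight of the point but does not answer it: low power is lost sensitivity, whereas confounding with run is bias with understated error.

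**Conclusion.** The concern holds as a gap in the plan: the order rule, with sequential dosing, permits dose group and time point to be confounded with SMFA run and possibly laboratory, and the SAP text states no term for either. With a group in one run, a true TRA of 80% could read 74-85% to 68-88%. Those ranges rest wholly on the assumed assay inputs. The error rates of 0.10-0.25 (t-test) and 0.15-0.53 (ANOVA) rest on the equal-variance assumption and on each group being its own run.

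The reach is limited. It would be wrong to infer that the dose effect as a whole may be an artefact: near 100% TRA the effect is a few points at most, and the contrast between groups 1 and 2 is far beyond it. The results at risk are group 1, late time points, the 50/80/90% counts and the IC80. The primary safety objective is untouched. The change should be made, because the remedy is cheap and these results feed the simulated regimens.

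**What to change.** 1. For the SMFA, replace the order sentence with a run plan for the frozen sera: all SMFA time points of a subject in one run, and subjects from at least two dose groups in each run. For sera already tested, use the second experiment that the SAP already permits as the balanced run.
2. State run (and laboratory, if two are used) as an effect in the TRA and concentration-TRA models, or state that the cited method already includes it.
3. Carry the control-feeder error into the TRA intervals. Balancing protects contrasts between groups but does not make the control more precise, and a subject's whole curve can still shift against the 80% line.
4. Reconcile Protocol 8.3.11 with 8.3.15, and name the laboratory whose result is the endpoint value; treat any other as replication.

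Cost: scheduling of stored sera, one or two model terms and a short text change. Some results arrive later than under the present rule. The layout is limited by run capacity, which the documents do not give. The simulated error rates near 0.05 apply to one subject of every group per run; a sparser layout relies more on the run term.

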### Sample size

Sample size calculations are based on assessing safety parameters. A total of twenty-five healthy adults (males and females) aged 18 – 35 will be divided over four groups. Each group will include five subjects. With the study's original sample size of n=20 (four intravenous groups of n=5), there is a 90% chance of observing at least 1 event if the true rate of such an event is 10.87% or more; and there is a 90% chance of observing no events if the true rate is 0.52% or less. The 5th (subcutaneous) group was pragmatically chosen to have the same size. Sample size for each group is appropriate for mAb infusion phase 1 trials based on similar trial designs for HIV, CMV, and anthrax monoclonal antibody prophylactic studies. Comparisons of the occurrence of adverse events and efficacy endpoints (e.g. antibody prevalence, density and transmission reducing activity) between study arms will be performed but the study is not specifically powered for this. Instead, TB31F pharmacokinetic parameters will be assessed by standard non-compartmental methods, using multiple observations per group and per study participant, and related to functional transmission reducing activity estimates (TRA).

### Statistical interim analyses and stopping guidance

There are no pre-defined criteria for study termination in this clinical trial but safety and reactogenicity data will be evaluated after each mAb TB31F administration before proceeding to the next group. A summary report of adverse events (AEs) will be provided to the SMC after all five groups have completed 84 days follow-up.

### Statistical Software

- Safety data analysis will be performed in IBM SPSS (latest version available), or R.
- SMFA data analysis will be performed in R.
- mAb TB31F pharmacokinetics will be analyzed using standard non-compartmental methods using the Phoenix WinNonlin software package.
- The relationship between plasma mAb TB31F concentrations and transmission reducing activity in SMFA will be assessed using standard compartmental pharmacokinetic models and empirical and mechanistic pharmacokinetic-pharmacodynamic models using the non-linear mixed effects modelling software package NONMEM 7.4, using Piraña 2.9 as an interface and R for data processing.

## Statistical Principles

### Confidence intervals and P values

Confidence intervals and P values are specified in protocol section 10 and will be based on 0.05 as significance level. Adjustments for multiple comparisons will be implemented where appropriate. Where applicable, normally distributed continuous outcomes will be presented as mean with 95% CI or standard deviations. Continuous outcomes that are not normally distributed will be transformed using a suitable transformation before reporting 95% CIs. Where a suitable transformation cannot be found, medians will be presented with interquartile ranges. For discrete (or count) data we will find interquartile ranges. Binary data will be presented as counts and proportions.

### Adherence and protocol deviations

Accounting for missing, unused and spurious data is described in protocol section 10.5. Briefly, missing data will not be imputed due to the small number of volunteers in each group. Subjects who miss an appointment date will not be removed from the study. Rather, their appointment and laboratory values will be recorded by appropriate missing value notation in the clinical database. Non-analyzable data will be documented in the deviations. A best-worst case sensitivity analysis may be performed.

## Study Outcome Measures

### Outcome Definitions

(Protocol section 2.3).

#### Safety outcome measures:

1. Number and severity of solicited local adverse events from the moment of first product administration through day 7
2. Number and severity of solicited general AEs from the moment of first product administration through day 28
3. Number and severity of clinically significant hematological and biochemical laboratory abnormalities from the moment of first product administration through day 28
4. Number and severity of unsolicited adverse events from first product administration through end of study
5. Number of serious adverse events from first product administration through end of study

#### Efficacy outcome measures:

6. TB31F mAb concentration in serum at different time-points post administration
7. Pharmacokinetic parameters of the TB31F mAb determined by non-compartmental analysis (e.g. maximum concentration ( $C_{max}$ ), terminal half-life ( $t_{1/2}$ ), area under the concentration versus time curve (AUC), volume of distribution ( $V_d$ ) and the absorption rate constant ( $K_a$ ) when TB31F is administered subcutaneously)
8. Transmission reducing activity (TRA) of participant serum at different time-points post administration, quantified as percentage reduction of oocyst densities in the presence of test serum as compared to control serum in standard membrane feeding assays (SMFA)
9. Transmission blocking activity (TBA) of participant serum at different time-points post administration, quantified as percentage reduction in oocyst prevalence in the presence of test serum as compared to control serum in standard membrane feeding assays (SMFA)

#### Other outcome measures:

10. Anti-drug antibody (ADA) levels in study subjects at different time-points post administration

## Analysis Methods

### Trial population

The primary safety and reactogenicity data will include all subjects who meet the eligibility criteria, receive study product mAb TB31F, and for whom safety, efficacy and immunogenicity data are available.

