8.3.14 Discontinuation of study procedures

Participants have the right to decline study procedures for any reason and at any time during the study. If a subject declines study procedures, this will be recorded as a study deviation and the reason will be clearly documented in the source document. The subject will be encouraged to complete all remaining safety related follow-up visits and procedures through the entire study period, including unscheduled visits. The reason for all discontinuations will be documented in source documents and the eCRF.

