If a subject withdrawal occurs for any reason, the investigator must make every effort to determine the primary reason for a subject's withdrawal from the study and record this information in the study file. However, in accordance with the principles of the current version of the Declaration of Helsinki, a subject does have the right to withdraw from the study at any time and for any reason and is not obliged to give his or her reasons for doing so.

With permission of the subject, all data generated before withdrawal will be included in final study analysis with subject's permission, unless it is felt that the data is compromised. Blood samples collected before withdrawal will be used/stored unless the subject specifically requests otherwise.

As a result of occurrence of an adverse event/serious adverse event

If any subject develops an AE/SAE leading to premature withdrawal, the event will be fully followed-up. For premature withdrawal in connection with the emergence of an AE/SAE that is considered to be clinically relatively favorable (for example, the diagnosis is known, and it is expected to be resolved completely within a week), intermittent follow-up may be accepted as long as the plan for follow-up of the event is fully described in the notes section of the subject's CRF. Follow-up visits will be carried out for all subjects who are withdrawn due to occurrence of an AE or in connection with a change in any other safety indicator (vital sign or clinical laboratory result).

All data generated before withdrawal will be included in final study analysis with subject's permission, unless it is felt that the data is compromised. Blood samples collected before withdrawal will be used/stored unless the subject specifically requests otherwise.

As a result of lost to follow-up

To prevent lost to follow-up, subjects will be reminded by phone, email, or text message of their next study visit. In the event of a missed visit, subject will be contacted by phone within 1 day. A

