10. STATISTICAL ANALYSIS

All data will be collected and verified prior to analysis. All data will be analyzed in accordance with the Statistical Analysis Plan. Final analyses of all data will occur after study completion and final verification of data according to GCP. All data analyses will be conducted using IBM SPSS and R using the latest version available. Detailed statistical procedures, listings, table shells, and figures will be provided in a SAP prior to analysis. The SAP will be finalized before study close-out and database lock. The following key statistical components will be considered and a detailed description will be documented in the SAP:

- Primary and secondary endpoints and how they will be measured
- Statistical methods and tests that will be used to analyze the endpoints
- Strategy that will be used if the statistical test assumptions are not satisfied
- Indication of whether the comparisons will be using one-tailed or two-tailed *t*-test (with justification of the choice) and the level of significance to be used
- Identification of whether any adjustments to the significance level or the overall P-value will be made to account for any planned or unplanned subgroup analyses or multiple testing

- Specification of potential adjusted analyses and a statement with which covariates or factors will be included
- Planned exploratory analyses and justification of their importance
- Any subgroup effects with biological justification and support from within and outside the study

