10.1 Primary study parameter(s)

The number of subjects enrolled, completed, or withdrawn will be summarized. Reasons for withdrawal, when known, will be provided. Demographic data will be summarized by descriptive statistics and will include total number of observations (n), mean, standard deviation (SD) and range for continuous variables, and number and percentages for dichotomous variables. The primary safety, and reactogenicity outcomes will include all subjects who meet the eligibility criteria, receive study product mAb TB31F, and for whom safety data are available.

Safety Analyses

For the safety analysis, data from all subjects who received a dose of mAb TB31F and for whom safety data are available will be included. All analyses will be descriptive. Data will be presented by dose, overall/dose and overall/subject. Results will be summarized by study group. The percentage of subjects with at least one local AE (solicited and unsolicited), with at least one general AE (solicited and unsolicited) and with any AE during the solicited follow-up period will be tabulated with exact 95% CI (two-sided). No multiplicity adjustment will be implemented in analysis. The same calculations will be performed for AEs rated as grade 3. The percentage of subjects reporting each individual solicited local and general AE during the solicited follow-up period will be tabulated with exact 95% CI. The same tabulation will be performed for grade 3 AEs and for AEs with relationship to mAb TB31F administration. The reports of unsolicited AEs will be reviewed by a physician and will be categorized by ICD-10. The percentage of subjects with at least one report of unsolicited AE and reported up to 28 days after mAb TB31F administration will be tabulated with exact 95% CI. The same tabulation will be performed for grade 3 unsolicited AEs and for unsolicited AEs with a relationship to mAb TB31F administration. SAEs will be described in detail. Withdrawals due to AEs/SAEs will also be summarized. Vital signs which are outside of the normal range and clinically significant will also be listed in tables. The frequency of signs and symptoms will be compared between groups with the chi-square test or fishers exact test. Serious adverse events (SAEs) occurring at any point during the trial will be summarized and relatedness to vaccine will be assessed.

Clinical Laboratory Data Analyses

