10.5 Accounting for Missing, Unused, and Spurious Data

The SAP will be followed even if data are missing. For the safety analysis, data from all subjects who received a dose of mAb TB31F in the study will be included. Subjects with missing data will not be imputed. Subjects who miss an appointment date will not be removed from the study. Rather, their appointment and laboratory values will be recorded by appropriate missing value notation in the clinical database. Non-analyzable data will be documented in the deviations.

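### The SAP's primary safety set requires efficacy and immunogenicity data, contrary to protocol 10.1 and 10.5, so a dosed subject with adverse event data but no post-dose ADA result falls outside it

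*SAP*

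**What the plan says.** The documents define the safety population in several places, and the definitions differ.

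- **SAP, Trial population.** The primary safety and reactogenicity data cover subjects who meet the eligibility criteria, "receive study product mAb TB31F, and for whom safety, efficacy and immunogenicity data are available". The SAP defines no other safety set.
- **Protocol 10.1, first paragraph.** This is nearly the same sentence, but the only data condition is safety data: "The primary safety, and reactogenicity outcomes will include all subjects who meet the eligibility criteria", if they were dosed and have safety data.
- **Protocol 10.1, Safety Analyses.** Here "data from all subjects who received a dose of mAb TB31F and for whom safety data are available will be included". Eligibility is not a condition.
- **Protocol 10.5.** For the safety analysis, "data from all subjects who received a dose of mAb TB31F in the study will be included".
- **Protocol 8.4.2, erroneous inclusion.** A wrongly included subject who has been dosed is followed for safety, but that subject's data are left out of the analysis.

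Protocol section 10 hands the analysis to the SAP: "All data will be analyzed in accordance with the Statistical Analysis Plan". The SAP refers to protocol 10.5 for missing data but does not repeat its all-dosed rule.

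The immunogenicity outcome in the SAP is outcome 10: "Anti-drug antibody (ADA) levels in study subjects at different time-points post administration".

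**The concern.** The SAP sentence is about safety data, yet it adds two conditions that have nothing to do with whether a subject's adverse events were observed. All three data types are joined by 'and', so a subject lacking any one of them fails the definition.

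Safety is the primary objective, with five subjects per group and no replacement after dosing (protocol 8.5). A subject removed from the set takes their AEs out of the numerators and themselves out of the denominators of the primary AE tables. Subjects who leave early or decline further bloods may do so because of an AE, in which case the missingness is related to the outcome being tabulated.

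A related conflict concerns eligibility. The SAP, the first paragraph of 10.1 and the erroneous-inclusion rule in 8.4.2 remove ineligible dosed subjects. The Safety Analyses paragraph of 10.1 and section 10.5 keep them.

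**Working it through.** **1. Who satisfies the protocol but not the SAP?**

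The efficacy condition would rarely bite. The SAP counts serum concentration as an efficacy outcome, and PK sampling starts at end of infusion. The immunogenicity condition is the one that matters. Outcome 10 counts only levels after administration, so the pre-dose ADA sample does not supply it. In the schedule (8.3.18) the first post-dose ADA sample is on day 7, whereas AEs are recorded from day 0. Three kinds of dosed subject can therefore have safety data and no post-dose ADA result:

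- (a) one who leaves before day 7;
- (b) one who declines research bloods before day 7 but stays for safety follow-up, as 8.3.14 intends: "The subject will be encouraged to complete all remaining safety related follow-up visits and procedures through the entire study period";
- (c) one who withdraws and permits use of the data but not of the samples. Section 8.4.2 allows this: "Blood samples collected before withdrawal will be used/stored unless the subject specifically requests otherwise".

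Protocol 10.3 differs from the schedule: it places ADA measurement at the PK time points, which would make the first post-dose sample end of infusion. On that version route (a) largely closes.

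**2. The plan's own figure.**

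Inputs from protocol 4.4: n = 20, event rates 10.87% and 0.52%.

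- Chance of at least one event: 1 − (1 − 0.1087)^20 = 0.900.
- Chance of no event: (1 − 0.0052)^20 = 0.901.

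Both reproduce the stated 90%.

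**3. Effect of one exclusion on the detectable rate.**

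The rate giving a 90% chance of at least one event is 1 − 0.1^(1/n).

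| n | Rate |
|---|---|
| 20 | 10.87% |
| 19 | 11.41% |
| 25 | 8.80% |
| 24 | 9.15% |

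This hardly changes.

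**4. Effect of one exclusion on AE proportions.**

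Intervals are exact (Clopper-Pearson) 95%, the type protocol 10.1 specifies. The groups 1-4 counts (2 of 20 with local solicited AEs, 12 of 20 with fatigue) come from protocol 13.2. The loss of one subject is an assumption. The last two rows are hypothetical counts.

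| Case | All dosed | One excluded, had the event | One excluded, no event |
|---|---|---|---|
| Local solicited AE, groups 1-4 | 2/20 = 10.0% (1.2-31.7%) | 1/19 = 5.3% (0.1-26.0%) | 2/19 = 10.5% (1.3-33.1%) |
| Fatigue, groups 1-4 | 12/20 = 60.0% (36.1-80.9%) | 11/19 = 57.9% (33.5-79.7%) | 12/19 = 63.2% (38.4-83.7%) |
| Single event in one dose group | 1/5 = 20% (0.5-71.6%) | 0/4 = 0% (0-60.2%) | not applicable |
| Single event, all groups | 1/25 = 4.0% (0.1-20.4%) | 0/24 = 0% (0-14.2%) | not applicable |

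Common events move by about two to three percentage points. A rare event can halve or disappear.

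**The case against.** The strongest reply is that the sentence is loose drafting and would not be applied literally.

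- The SAP's Purpose section calls it a supplement to the protocol, so one sentence need not override 10.1.
- A dosed subject without ADA is a missing-data case. Protocol 10.5, to which the SAP refers, keeps all dosed subjects, and 8.4.2 keeps data generated before withdrawal, with the subject's permission.
- The SAP elsewhere tabulates AEs for the whole study population and computes PK for each subject who received the antibody.
- The report on groups 1-4 in protocol 13.2 uses all 20 dosed subjects as its denominator.
- The affected subject would be uncommon, the size of the effect rests on an assumed loss, and the SAP does not define when data count as available.
- Serious adverse events and withdrawals due to AEs are summarised separately, and the holding rules and the Safety Monitoring Committee's review do not use this set.

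Much of this stands as a limit on impact. The all-dosed reading may well be what was meant, and for a subject who misses only some research bloods exclusion is a risk rather than a certainty. None of it removes the conflict. Protocol section 10 directs that the analysis follow the SAP, and the SAP's summary of 10.5 covers non-imputation and missed visits without restoring the all-dosed rule. The SAP therefore contains an explicit rule for the primary safety data that contradicts the protocol.

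**Conclusion.** The concern holds. The SAP makes the primary safety set depend on efficacy and immunogenicity data, whereas protocol 10.1 and 10.5 do not. The contradiction is certain; its numerical effect is conditional. It requires a dosed subject with safety data and no post-dose ADA result, which follows from the day 7 sampling in 8.3.18 and from counting ADA only after administration, as outcome 10 does.

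If such a subject occurs, the damage is confined to AE proportions and their intervals. It is negligible for common events and for the detectable rate, but it can erase the only event in a group of five.

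The eligibility condition and the 8.4.2 exclusion are a separate inconsistency with the all-dosed statements and need settling at the same time. This should be fixed before database lock.

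**What to change.** 1. In the SAP, define one safety set: all subjects who received any amount of TB31F, analysed by the dose and route received.
2. In the SAP's Trial population section, delete the efficacy and immunogenicity conditions and the eligibility condition. Delete the eligibility condition from the first paragraph of protocol 10.1.
3. In protocol 8.4.2, state that wrongly included subjects who were dosed stay in the safety set, flagged, and may be excluded only from PK and pharmacodynamic analyses.
4. Define separate PK, membrane-feeding and ADA sets. Apply data-availability conditions only to these, and say for each which post-dose samples count.
5. Reconcile the ADA time points in protocol 10.3 with the schedule in 8.3.18.

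The cost is SAP and protocol wording. No extra data, samples or visits are needed.
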